#### Obtaining blood samples:

Mild bruising and pain is possible

#### Obtaining nasal swabs:

The nasal swabs require the insertion of a swab inside the nose. This can be uncomfortable and can cause temporary runny nose and sneezing in some people.

#### Loss of confidentiality

### **15. RISK MANAGEMENT PROCEDURES AND ADEQUACY OF RESOURCES**

Subjects will be monitored throughout the study and their symptoms will be recorded and reviewed by the medical monitor on a daily basis during the active phase of treatment.

Safety of the study medication will also be assessed through laboratory data collection either at the end of the treatments (for non-hospitalized patients) or on hospital admission (utilizing labs on admission for hospitalized patients)

Study participants will be advised to report any skin eruptions to the study team and to stop medication immediately until they can be interviewed by our medical monitor who will make the assessment of allergy.

Respiratory allergies such as asthma exacerbations will be treated as COVID-19 exacerbations, where medication will be stopped and participants will be directed to immediate medical attention. An adverse event will be logged, and relation to the study medication will be determined per protocol.

In an event of participants requiring immediate medical attention, the study team will first refer the patient to contact their primary care physician if they are in close communication. If they are not, the study team will provide the participant with a short list of telephone numbers that patients can call to seek immediate medical attention. This will be specific to Southern California and will include 24-hour hotlines that are run by insurance companies, healthcare centers, and regional governments. If none are appropriate, they will be directed to dial 911.

All serious adverse events (SAEs) will, per UCSD IRB guidelines, be reported to the IRB and DSMB within 3 business days of learning of the event. The study biostatistician will send a tabulated symptom and adverse event report daily to all sites and to the study PI and weekly to the study DSMB and IRB.

Any adverse events, as well as any escalation of care, including urgent care, emergency room, or hospitalization, will be reported to the study team after appropriate medical care has been received, via a dedicated phone number or email address that is specific for urgent matters.

The UCSD site will implement a Data and Safety Monitoring Board (DSMB) to review data safety and monitoring as part of their responsibilities. The DSMB will include two senior researchers, and a consumer representative. They will have a conference call bi-weekly (or more frequently, if needed).

To address loss of confidentiality and data security risks all data management tasks will be performed by the KCIR Data Core in compliances with all UCSD and Federal regulations. A comprehensive menu driven data management system is already developed for all KCIR funded studies using Microsoft Access software. This system is located within the UCSD Health Science computer network with limited access and DUO authentication system. This system provides a stable and secure platform for: a) study data input, validation, edit and query; b) subject tracking system for all subjects' study activities (screening and study visits); c) data storage, compilation, selection, and summary transfer to various statistical/graphical software. We are also planning on using UCSD REDCap forms to collect data from subjects. All subjects are assigned a unique ID number. Patient names are never used in conjunction with the unique clinic ID number. The single name-to-ID relational file is kept in an encrypted form electronically and in a locked filing cabinet physically. Statistical analysis will be conducted using SPSS software package. All statistical transfer routines are inherently secure via their operating platform and they contain no patient names or personal data.

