### **Sub-studies 1a and 1b**

Once enrolled, all study participants will receive a package containing the following:

- 14 day supply of study medication (capsules containing either FoTv or mQFPD or placebo)
- Digital thermometer
- Urine pregnancy test (for women of child bearing potential)
- Written instructions on proper usage of study medication
- Paper study daily diary, to include daily medication diary, symptom scores, and temperature/BP measurement data
- A blood pressure cuff or glucometer will be provided to study subjects who require but do not possess one. The study participants are not responsible for lost, stolen, or damaged devices

The study package will be sent via local courier or phlebotomist who will coordinate directly with the study participant to complete delivery. Missed doses will be logged in the provided medication diary, remain unused, and be accounted for at the end of the study. Participants will continue to make every effort to maintain quarantine through vigorous hand washing and appropriate self-isolation measures. All study participants will also receive instruction to strictly avoid alcohol, cannabis, and dairy products during the study period.

During the trial period, participants will be verbally instructed on proper usage of study product, asked to take their temperature twice daily until they reach two consecutive afebrile readings. Participants with prior hypertension will also be required to take daily home measurements of their blood pressure and report any measurements of SBP <90 or >150, or DBP >90 directly to the study team. Any measurements of SBP below 80 or above 180 will be advised to seek immediate medical attention (as specified in Section 15). Participants with prior diabetes will take daily morning glucose measurements and report any blood glucose measurement >200 directly to the study team. Any measurements of blood glucose below 70 will be advised to eat a carbohydrate rich food and report to the study team, and measurements persistently below 70 will be advised to seek immediate medical attention as an immediate priority prior to reporting to the study team. Participants with congestive heart failure or using diuretics will take daily morning weight measurements using a home scale and report to the study team any weight change greater than 3 lbs (1.5 kg) during the study period.

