### 5. Vital Signs (to be collected for participants of sub-studies 1a and 1b only):

- Body temperature will be self-reported at Study Treatment Day 1, daily throughout the treatment period until two consecutive afebrile results are seen, and again at the End of Study Treatment Day 14.
- Study participants with a baseline diagnosis of hypertension will be instructed to take daily blood pressure measurements using a home blood pressure cuff. If they do not have access to a home blood pressure cuff, members of the study team will purchase one online and have it sent next-day. They are to contact the study team with any measurement of systolic blood pressure above 150 or below 90, as well as diastolic measurements above 90. Any measurements of SBP below 80 or above 180 will be advised to seek immediate medical attention as specified in section 15.
- Study participants with a baseline diagnosis of diabetes mellitus who are on insulin or sulfonylureas will be instructed to take blood sugar measurements in the morning, as well as three times daily before meals. If they do not have access to a home glucometer, members of the study team will purchase one online and have it sent next-day. Any measurements of blood glucose below 70 will be advised to eat a carbohydrate rich food and report to the study team, and measurements persistently below 70 will be advised to seek immediate medical attention as an immediate priority prior to reporting to the study team.
- Study participants with a baseline diagnosis of congestive heart failure or diuretic use will be required to monitor their weight daily and notify the study team if their weight changes by greater than 3 lbs (or 1.5 kg) throughout the 14 day trial period. If they do not have access to a home scale, members of the study team will purchase one online and have it sent via next-day delivery.
- Study participants who are not hospitalized yet remain febrile and report ongoing symptoms at EOT visit (Day 14) will continue to take their temperature and be contacted every 2-3 days by members of the study team until they are no longer symptomatic and are afebrile.

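### Sub-studies 1a/1b: for participants needing immediate medical attention, Section 15 puts 911 after primary care (if in close contact) or hotlines, with no exception for the four symptoms the protocol says require hospitalization

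*Combined protocol and SAP*

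**What the plan says.** Section 15 (Risk Management Procedures and Adequacy of Resources) gives one referral order for a participant who needs urgent care:

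1. "In an event of participants requiring immediate medical attention, the study team will first refer the patient to contact their primary care physician". The condition on this step is "primary care physician if they are in close communication".
2. "If they are not, the study team will provide the participant with a short list of telephone numbers". The list "will include 24-hour hotlines that are run by insurance companies, healthcare centers, and regional governments".
3. "If none are appropriate, they will be directed to dial 911".

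The same section says that respiratory allergies such as asthma attacks "will be treated as COVID-19 exacerbations, where medication will be stopped and participants will be directed to immediate medical attention". For skin eruptions, it tells participants to stop study medication until the medical monitor has interviewed them.

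Section 9 refers to this order for blood pressure. Under Vital Signs: "Any measurements of SBP below 80 or above 180 will be advised to seek immediate medical attention as specified in section 15". The text headed Sub-studies 1a and 1b says the same.

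Section 9, Adverse Events, adds that worsening cardiac or pulmonary status is escalated at once to suitable care, and that anyone hospitalized stops study medication. The next bullet refers any symptom on the coordinators' COVID-19 list to the participant's primary care provider.

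Section 10 excludes from 1a and 1b anyone with trouble breathing, persistent chest pain or pressure, new confusion or inability to be aroused, or bluish lips or face. It attributes to the CDC the statement that these symptoms require hospitalization.

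**The concern.** The referral order begins once a participant is already known to need urgent care, yet the emergency number comes at its end. The protocol identifies four symptoms as grounds for hospital care but uses them only to keep people out at entry. If one of them appears during treatment, the written instruction to the study team is still a call to primary care or to a hotline, possibly one run by an insurer.

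This matters because participants are at home and Section 16 says the intervention is mostly conducted remotely. Coordinators speak with participants daily (Section 9, Adverse Events), so they may be the first to hear of such a symptom and would work from the written order. What is at stake is delay in reaching emergency care.

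Each sub-study has its own reason for care. In 1a, Section 14 records the FDA's concern that FoTv could worsen COVID-19. In 1b, the product contains ephedrine, and Section 14 relies partly on daily blood pressure readings in hypertensive participants to manage that risk; an extreme systolic reading is then handled through this same order.

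**Working it through.** No arithmetic applies. The check is whether any text supplies a direct emergency route for the four symptoms or for extreme blood pressure.

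**The order itself (Section 15).** A participant in close contact with a primary care physician is sent to that physician first. A participant who is not is given the telephone list. In both branches 911 comes last of the three options. Read literally, the list and then 911 follow from the branch without close primary-care contact; a wider reading lets 911 apply to both. Neither reading moves 911 forward, and none of the four symptoms is named as an exception.

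**Respiratory sentence (Section 15).** It requires medication to stop and directs the participant to immediate medical attention. That is the condition which starts the referral order, so it adds a stop but no separate route.

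**Immediate escalation (Section 9, Adverse Events).** Set against the four symptoms:

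| Symptom (Section 10) | Within cardiac or pulmonary deterioration? | Route named? |
|---|---|---|
| Trouble breathing | Plausibly yes | No |
| Persistent chest pain or pressure | Plausibly yes | No |
| Bluish lips or face | Plausibly yes | No |
| New confusion or inability to be aroused | Not clearly | No |

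The escalation sentence therefore supports urgency for three of the four, but does not say where the participant goes. The bullet that follows points listed COVID-19 symptoms to primary care without a severity limit. The list is not in the documents, so whether it contains any of the four cannot be checked.

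**Extreme blood pressure (Section 9, two places).** Systolic readings below 80 or above 180 are explicitly referred to Section 15 and so take on its order. The glucose rule nearby is written differently: for readings persistently below 70, the participant is told to seek care before reporting to the study team.

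**Elsewhere.** No instruction to go directly to 911 or to an emergency department was found in any other section.

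**The case against.** The strongest reply is that the order is softer than it looks. The primary-care step is conditional. The 911 step depends on whether the other options are suitable, not on their having been tried and failed. A sensible coordinator would judge a hotline unsuitable for a participant with blue lips and go straight to 911. Section 9 already requires immediate escalation of cardiac or pulmonary deterioration. Participants report escalations of care after receiving care, so they are free to go to an emergency department first. A study physician can be reached by telephone at all hours, and the medical monitor reviews symptoms daily.

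Much of this stands. It narrows the exposed case to a participant whose first contact is the study team, most clearly one in close contact with a primary care physician. It does not change the written order, and a safety instruction should not depend on staff reading an exception into it.

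Several stronger readings are tempting, but the documents do not support them:

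- *Participants lack emergency instructions.* Consent pages were removed, and the written participant instructions and coordinator lists are not included. Only the protocol text can be judged.
- *Medication continues through most of these symptoms.* Section 15 stops medication for a COVID-19 exacerbation but does not define the term. All four symptoms could fall under it, so a count of which are covered would be arbitrary.
- *Harm can be sized from the hospitalization share in Section 14 (approximately 19%).* That figure covers COVID-19 cases generally, whereas 1a and 1b enroll mild-to-moderate cases. It counts hospitalizations, not these symptoms or calls made first to the team.
- *Onset can be placed on particular dosing days from the 5-7 day window in Section 7.* Entry is also allowed within 9 days of symptom onset, and the documents do not fix the interval between diagnosis and first dose.

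**Conclusion.** The point holds and should be fixed. For a participant in 1a or 1b already judged to need immediate medical attention, the only stated route puts 911 last, after primary care or a hotline list. It makes no exception for the four symptoms the protocol itself links to hospitalization, and systolic readings below 80 or above 180 are sent into the same order. The immediate-escalation sentence plausibly reaches three of the four symptoms but gives no route, and it does not clearly reach new confusion or inability to be aroused.

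The size is one instruction in one section, with two cross-references to it. No rate of these symptoms on treatment is given, so the number of participants affected cannot be stated. The conclusion assumes that staff follow Section 15 as written and that no unseen instruction overrides it. This is a safety-procedure defect; it does not bear on the validity of the statistical analysis.

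**What to change.** 1. In Section 15, before the referral order, state that trouble breathing, persistent chest pain or pressure, new confusion or inability to be aroused, or bluish lips or face goes directly to 911 or an emergency department. Study medication is held pending medical-monitor review, as is already done for skin eruptions, and the study physician is notified afterwards.
2. In Section 9, Adverse Events, cite this rule as the route for immediate escalation, and limit referral to primary care to non-urgent symptoms.
3. State the route for systolic pressure below 80 or above 180 in the same place in Section 15, since both Section 9 references point there.

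The cost is protocol wording and matching instructions for coordinators and participants, with no new data, visits or patients. The downside is a few temporary medication holds. These are reversible, but could slightly affect completion, which is a primary feasibility outcome in both sub-studies; recording each hold and its outcome would keep that effect visible.

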## **16. PRIVACY AND CONFIDENTIALITY CONSIDERATIONS INCLUDING DATA ACCESS AND MANAGEMENT**

To maintain confidentiality, all laboratory specimens, evaluation forms, reports and other records will be identified on the basis of a coded number only. All study records will be kept in a locked file cabinet and code sheets linking a patient's name to a patient identification number will be stored separately in another locked file cabinet. Clinical information will not be released without written permission of the participant, except as necessary for monitoring by the FDA or IRB. The Principal Investigator will also comply with all applicable privacy regulations.

Email communication with patients will be conducted using encrypted email, or via MyChart.

Data will be entered into Microsoft Access or CTRI RedCap where it will be stored on the university server with access available to the Principal Investigator, data manager, and biostatistician. Only the research team will have access to the data. All communications will be conducted using UC secure systems with multiple identification checks.

The UCSD site will be responsible to provide data management support and will conduct all data analyses except for hospital record acquisition and adjudication of all study participants across all sites, which will be conducted at UCI and data sent to UCSD for analysis. We will establish a publication committee that includes among others each member, each study site PIs and the study statistician. It is the responsibility of this committee to approve and oversee all analyses, presentations and publications related to this project.

The majority of study consenting and conducting the study intervention will be done remotely by the study team at UCSD, although available staff at UCI and later UCLA sites may be asked to contribute to this effort. Otherwise, the UCI and later UCLA sites will be primarily responsible for recruitment of study participants.

## **17. POTENTIAL BENEFITS**

For the study participant, FoTv and mQFPD may potentially provide direct benefit by reducing the severity of their illness as measured by duration of fever, risk of hospitalization, intubation or death.

Fo-Tv can potentially accelerate, prolong, or enhance the quality of immune responses to vaccine antigens and improve the efficacy of vaccines in individuals with reduced or weakened immune responses as measured by laboratory testing and/or reduce severity of vaccine side effect profile as measured by symptoms scoring.

It is also possible that there may not be any direct benefit for study participants.

## **18. RISK/BENEFIT RATIO**

The most significant potential benefit of this study is to contribute to the possible future availability of safe and inexpensive agents for the treatment of COVID-19. This study will generate important safety data needed to subsequently evaluate the efficacy of FoTv and mQFPD in time to provide guidance for the use of these medicines during the current pandemic.

Furthermore, the collaborations formed as part of this study will provide a foundation for future studies evaluating the safety and efficacy of similar therapeutics for treatment of active COVID- 19, and the application of these therapeutics for more severe manifestations of disease.

For the study participant, FoTv or mQFPD may potentially provide direct benefit by potentially reducing the severity of their illness as measured by duration of fever, risk of hospitalization, intubation or death. Due to the high mortality associated with COVID-19, the benefits of participation in the trial outweigh the potential risks as outlined above in the background and risks sections.

The other most significant potential benefit of this study is to contribute to the possible future availability of safe and inexpensive agents for adjunctive therapy of COVID-19 vaccination.

For the study participant, FoTv may potentially provide direct benefit by potentially reducing the severity of their symptoms or improving vaccination response. Due to the high mortality associated with COVID-19 and the high concerns of vaccine hesitancy due to side effect burden, especially during upcoming public health campaigns for booster immunizations, the benefits of participation in the trial outweigh the potential risks as outlined above in the background and risks sections.

## **19. EXPENSE TO PARTICIPANT**

There is no cost to the participant.

## **20. COMPENSATION FOR PARTICIPATION**

In compensation for subject's time and efforts they might receive up to \$250 for sub-studies 1a and 1 b, and up to \$200 for sub-study 1c for entire study participation. It will be paid in gift cards as following:

Sub-studies 1a and 1b: will receive \$50 at the beginning of the study and \$100 after 14 days of taking study medication. They will also receive an additional \$100 bonus at the study completion after second follow up at day 58. They will also receive a thermometer for their participation, which they will be allowed to keep.

Sub-study 1c: participants will receive \$50 at the beginning for the study, \$50 at each of the follow up at 2 and 4 weeks; and a final \$50 at 12 months after the study baseline.

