Each participant will receive a paper copy and an emailed study daily diary requesting this information (temperature readings, blood pressure and/or glucometer readings) as well as symptom scores, and medication compliance. This survey (daily diary) will be generated directly through the study database and will interface directly with the secured study database. Participants who are unable to respond to emails will be allowed to record data into the provided paper diary and report the information at the completion of the study to a member of the study team by phone or photo at intervals specified below. Once this information has been reported, there will be no need for the study team to collect the diary.

Any adverse events, as well as any escalation of care, including urgent care, emergency room, or hospitalization, will be reported to the study team after appropriate medical care has been received, via a dedicated phone number or email address that is specific for urgent matters. A dedicated phone number will be available throughout the entire study period to call a physician member of the study team who is available 24 hours a day, 7 days per week, for urgent matters. Non-urgent messages will be routed to a dedicated email address or study coordinator.

If a study participant is hospitalized as a result of COVID-19, the participant will be instructed to discontinue study medication and the study team will follow up with either the patient or the emergency contact at the end of the trial period, or following the hospitalization, to determine final outcome and obtain laboratory records from the hospitalization.

At Day 14, a telephone call will be conducted among participants who have not been hospitalized to assess for COVID-19 symptoms, review any adverse events, review concomitant medications, drug accountability (participants will take pictures of

their empty bottles and send to the study team), and harmonize any data discrepancy between their daily diary and the study database. At this time, they will have completed the investigational product.

At the time of the Day 14 telephone call, participants who have not been hospitalized will be directed to obtain end-of-trial blood draw via outpatient laboratory or in-home phlebotomy.

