### 6. Adverse Events

- Adverse events are being monitored in three formats: daily communication with study team to report symptoms and adverse event reporting as described elsewhere (see section 15), labs at the end of the 14-day treatment period, and urgent reporting of adverse events via a 24 hour physician staffed phone line (see below). The study team will have a daily communication with subjects where our study coordinators will review all subjects' symptoms and their severity. This information will be tallied daily and will be reported to each site's PI and study main PI and medical monitor. Furthermore, they will be reported to the study DSMB and IRB.
- Information regarding occurrence of adverse events will be captured on the IRB approved standard case report form (CRF) as follows: Duration (start and stop dates and times), severity/grade, outcome, and relation to study medication).

- Any deterioration in cardiac or pulmonary status will be immediately escalated to proper medical attention and that any study participant who is hospitalized for any reason will be required to stop study medication irrespective of the cause of this adverse event. These events will subsequently be reported to the DSMB and IRB for review.
- A list of anticipated side effects of FoTv or mQFPD will be available to study coordinators, as will a list of known symptoms of COVID-19. Any reported symptom on the COVID-19 list will be referred to the study participant's primary care provider.

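### In sub-studies 1a and 1b, $100 of the $250 payment is worded as depending on 14 days of dosing, and nothing says that participants told to stop are still paid

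*Combined protocol and SAP*

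**What the plan says.** Section 20 of the combined protocol and SAP sets a maximum of $250 for sub-studies 1a and 1b and introduces it with the words "In compensation for subject's time and efforts they might receive up to" that amount. It has three instalments: $50 "at the beginning of the study and" $100 "after 14 days of taking study medication", then a $100 "bonus at the study completion after second follow up at day 58". There is no pro-rata rule, no forfeiture rule and no statement about participants who stop early.

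For sub-study 1c the same section attaches the intermediate $50 payments to contacts: "at each of the follow up at 2 and 4 weeks".

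The stopping instructions are elsewhere:

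- Section 9, under Sub-studies 1a and 1b, on admission for COVID-19: "the participant will be instructed to discontinue study medication".
- Section 9, Clinical Assessments, item 6 (Adverse Events): any participant "hospitalized for any reason will be required to stop study medication".
- Section 15: "Study participants will be advised to report any skin eruptions to the study team and to stop medication immediately". That sentence goes on to limit the stop to the time until the medical monitor has interviewed the participant. Section 15 also stops medication for respiratory allergies.

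Section 6 makes safety and feasibility the primary objectives of 1a and 1b, with recruitment and completion rates as the feasibility focus. Section 9, Statistical Methods and Considerations, adds adherence and retention to the main analytic aims and takes adherence from case report forms and participant diaries. At Day 14, drug accountability rests on photographs of empty bottles taken by the participants themselves.

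**The concern.** The payment condition names the act of taking medication, while three other places in the protocol tell some participants to stop taking it. A participant deciding whether to mention a rash, or whether to record doses as missed, could reasonably think that $100 depends on the answer.

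This matters more here than in many trials because the possible incentive acts on what 1a and 1b are meant to measure. The two sub-studies exist to learn whether 24 capsules a day for 14 days is safe, tolerable and feasible before Phase 2. If the wording changed behaviour at all, reported reactions would go down and reported dosing would go up, and both would make the product look easier to take than it is. The wording also sits awkwardly with section 20's own basis for payment, which is time and effort. A non-hospitalized participant who has stopped still has the Day 14 call and blood draw to complete.

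**Working it through.** **1. Reproduce the plan's totals (section 20).**

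- 1a/1b: 50 + 100 + 100 = $250, which matches the stated maximum.
- 1c: 50 + (2 × 50) + 50 = $200, which also matches.

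**2. Share worded around dosing.** 100 / 250 = 0.40, or 40%.

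**3. Payment to a participant who stops permanently as directed but stays to day 58.**

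| Reading of section 20 | Start | Day 14 | Day 58 | Total |
|---|---|---|---|---|
| Literal: 14 days of dosing required | $50 | $0 | $100 | $150 (60%) |
| Time point: payable once day 14 is reached | $50 | $100 | $100 | $250 (100%) |

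The difference is $100 per person. The documents do not say which reading applies.

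**4. Can the effect on the outcomes be sized?** Two quantities would be needed: the rate of required stops (r), and the share of those participants who would report full dosing anyway (s). The documents give neither. If completion were counted from reported dosing, the reported rate would be (1 − r) + r·s and the inflation r·s. With purely assumed values:

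| r (assumed) | s (assumed) | True | Reported | Inflation |
|---|---|---|---|---|
| 5% | 10% | 95.0% | 95.5% | 0.5 points |
| 10% | 25% | 90.0% | 92.5% | 2.5 points |
| 19% | 50% | 81.0% | 90.5% | 9.5 points |

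The 19% borrows the hospitalization figure for severe disease in section 14 as an upper end. It is not a predicted stop rate for this population. The range of 0.5 to 9.5 points shows only that the size is undetermined, and no row is supported over another.

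**5. Cost of the change.** If k participants in a sub-study stop early, would have gone unpaid under the literal reading and complete the Day 14 contact, the added cost is $100 × k. If the intention was always to pay them, the cost is $0.

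**The case against.** The strongest reply is that the phrase simply marks a date. The three instalments read naturally as start, end of treatment and day 58. Section 9 uses the end of medication as a calendar label elsewhere: it places the day 28 call 14 days after medication ends for everyone, including hospitalized participants who were told to stop. Nothing in the documents says that the $100 is withheld, and the consent form, which may settle the matter, was not among the material reviewed. This stands. Forfeiture is a possible reading and not an established rule.

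Safeguards also exist: daily coordinator review of symptoms, daily review by the medical monitor, Day 14 laboratory tests and hospital records. Hospitalization in particular is hard to conceal. This stands in part. Daily review still depends on what participants say, and a photograph of an empty bottle does not show that the capsules were swallowed. Section 9 is also inconsistent about participants without email: one paragraph has them contacted daily, another lets them report at study completion.

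The contrast with 1c is limited. Dosing there lasts four days, so payments at 2 and 4 weeks could not have marked the end of treatment. It shows only that contact-based wording is already in use in the same section.

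A reader might infer more than the documents allow:

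- **That hospitalized participants have no contact at which to be paid.** Section 9 provides follow-up with the patient or emergency contact at the end of the trial period or after the admission, and includes them in the day 28 call.
- **That a rash necessarily costs the $100.** The stop in section 15 lasts until the medical monitor's interview and may be temporary.
- **That those who stop lose their reason to stay in follow-up.** The day 58 payment does not depend on dosing.
- **That the arms are biased differently.** Payment is identical in both blinded arms, so a between-arm effect would need different stop rates, which is conjecture.
- **That the 20% dropout allowance gives the number affected.** Dropout from the study is not the same as a required stop in someone still being followed.

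**Conclusion.** The point holds as an ambiguity worth removing. Section 20 words 40% of the maximum payment in 1a and 1b as following 14 days of dosing and is silent on participants who stop because the protocol directs it. Read literally, a permanent stop could cost $100 of $250. Given self-reported doses and symptoms, and primary or main aims of safety, completion and adherence, that may create an incentive in the favourable direction.

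It does not go further than that. Under-reporting and inflated adherence are plausible risks and have not been shown. Completion is not defined as 14 days of dosing; if it means remaining to day 58, this instalment bears on it only indirectly. The conclusion rests on the literal reading being one that participants could take, and on no clearer statement appearing in the participant information. The size of any effect is unknown. Severity is minor.

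**What to change.** Reword section 20 so that in 1a and 1b the $100 is paid at the Day 14 contact or, for hospitalized participants, at the follow-up already described in section 9, whether or not study medication was stopped. Put the same statement in the participant information, so that it is known at enrolment that reporting a reaction or stopping medication does not reduce the payment. No stopping instruction needs to change.

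While that paragraph is open, reconcile its description of day 58 as the second follow-up with section 9, where day 28 is the second call and day 58 the third.

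The cost is one sentence in section 20 and a matching one for participants. The $250 maximum is unchanged. The only added expense is $100 for each early stopper who would otherwise have gone unpaid, and nothing if they were always meant to be paid.
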